## 5 Data Analysis

The hypotheses of this study are:

1. In children with acute gastroenteritis, probiotic administration in the emergency department will be associated with a clinically-important decrease in the proportion of children suffering from moderate-severe disease, defined by a validated Modified Vesikari Score  $\geq 9$ , compared to placebo.
2. In children with acute gastroenteritis, probiotic administration will not be associated with serious adverse events, and will have a similar rate of side effects (e.g. bloating, fever) as compared to placebo-treated children.

All analyses will be undertaken by the intention-to-treat (ITT) principle, except for adverse events, which will use the as-treated principle (compare the subjects based on the treatment regimen that they received). Patients who drop out or inadvertently crossover will be followed and included in the ITT analysis. All statistical tests of hypotheses will be two-sided. Baseline characteristics will be analyzed to determine if there is a need to adjust for differences between groups in exploratory analyses. Sensitivity analyses will be performed to assess the possibility and consequences of non-random loss to follow-up. The proportions of children experiencing an unscheduled healthcare visit or any potential adverse effect, as reported by the caregivers, will be compared between groups using the Mantel-Haenszel test, stratified by site. The analysis will evaluate the presence/absence of pre-specified side effects, as an aggregate outcome variable. A per-protocol analysis will be conducted to provide additional insight as non-compliance may result in an underestimation of the benefits of probiotics in the ITT analysis.

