# 2 Study Objectives and Outcomes

## 2.1 Study Objectives

### 2.1.1 Primary Objectives

The primary objectives of the Probiotics trial are:

1. to test the hypothesis that, in children with acute gastroenteritis, probiotic administration in the emergency department will decrease the likelihood of moderate-severe disease, defined by a validated Modified Vesikari Score (MVS)  $\geq 9$ , compared to placebo.
2. to test the hypothesis that, in children with acute gastroenteritis, probiotic administration will not be associated with serious adverse events, and will have a similar rate of side effects (e.g., bloating, fever, abdominal distention) as compared to placebo-treated children.

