### 2.2.2 Safety Outcomes

Safety outcomes are:

1. The occurrence of invasive disease (including meningitis and bacteremia) from *Lactobacillus rhamnosus*.
2. Occurrence of side effects: bloating, gas, intestinal rumbling, diarrhea, blood in stool, abdominal pain, abdominal cramps, nausea, vomiting, loss of appetite, heartburn, constipation, skin rash, diaper rash, fever, nasal congestion, runny nose, sore throat, cough, headache, muscle aches, chills, weakness.

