## 7.4 Safety Outcomes

### 7.4.1 Side-Effects

The occurrence of any side-effect (listed previously) will be analyzed as a dichotomous variable for two time windows: the initial disease window (through day 14, or until resolution of symptoms) and through day 35 (which includes the initial window). The first of these two windows will not count diarrhea, vomiting, fever, or diaper rash as these will likely be experienced by a vast majority of subjects and are part (with the exception of diaper rash) of the primary and secondary outcomes. The latter window will only count diarrhea, vomiting, fever, or diaper rash that occur after the initial disease window.

The outcome will be compared between treatment groups using a Mantel-Haenszel test, stratified by center and duration of symptoms prior to randomization.

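### The side-effect objective asks for similarity, but the SAP specifies only a difference test on an any/none composite, with no confidence interval or margin and no stated per-term method

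*Combined protocol and SAP*

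**What the plan says.** SAP 2.1.1 makes side effects half of the second primary objective: the probiotic "will have a similar rate of side effects (e.g., bloating, fever, abdominal distention) as compared to placebo-treated children". Protocol section 5 has the same hypothesis: "will have a similar rate of side effects (e.g. bloating, fever) as compared to placebo-treated children". Neither says how close the rates must be to count as similar.

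SAP 2.2.2 lists the terms, beginning "Occurrence of side effects: bloating, gas, intestinal rumbling, diarrhea, blood in stool, abdominal pain, abdominal cramps, nausea, vomiting"; the full list has 23. SAP 7.4.1 then says "The occurrence of any side-effect (listed previously) will be analyzed as a dichotomous variable for two time windows".

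- **Initial disease window.** "The first of these two windows will not count diarrhea, vomiting, fever, or diaper rash", so 23 - 4 = 19 terms count.
- **Through day 35.** All 23 terms count, but those four only if they occur after the initial window.

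For the analysis itself, 7.4.1 says "The outcome will be compared between treatment groups using a Mantel-Haenszel test, stratified by center and duration of symptoms prior to randomization". It mentions no risk difference, interval, margin or analysis by term.

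Three other places bear on the point:

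- Protocol 5.1, under Specific Aim 2, plans to tabulate the listed side effects and compare them by arm, without naming a method.
- SAP 7.4.2 generally keeps these symptoms out of the adverse-event summaries, because they are reported separately.
- SAP 7.2 promises effect-size summaries and mentions dichotomous outcomes in general, but in the primary-outcome section and without naming an interval.

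**The concern.** The question and the method do not match. A Mantel-Haenszel test of equality can give evidence that the arms differ. When it is not significant, it does not say how large a difference remains possible. Only an interval, with or without a margin, answers that.

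Pooling the terms adds a second difficulty. A rise in one side effect moves an any/none outcome only through children who have none of the other side effects. The SAP accepts this for the initial window, where it drops four symptoms because nearly all children would have them. It keeps nausea, loss of appetite, abdominal pain and cramps, which can also belong to the illness. If many children have at least one of these, little room is left for a drug effect to show.

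At stake is what the report can say about tolerability: whether a clinically relevant increase has been excluded, and whether a change in one symptom such as bloating is assessed by a method fixed in advance.

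**Working it through.** **Inputs from the documents.** 970 randomized 1:1 (protocol), which is 485 per arm. With the planned 10% loss, 970 × 0.90 / 2 = 436.5, taken as 436 per arm. The SAP still gives 900 (450 per arm), which lies between the two. Tests are two-sided. No alpha is stated for side effects; 0.05 is assumed.

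**Inputs assumed.** The documents give no side-effect rates, so every rate below is an assumption. Stratification is ignored.

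**Check of the formula on the plan's own figure.** The pooled two-proportion formula without continuity correction, at 25% against 15%, alpha 0.05 and 90% power, gives 335 per arm, or 670. This matches the SAP exactly. The same formula reproduces all eight rows of the SAP 3.3 power table to within 0.005. All of that power is for the primary efficacy outcome.

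**1. What the difference test says about similarity.** Power = Φ[(d - 1.96·SE0)/SE1], where SE0 = √(2p̄(1-p̄)/n) and SE1 = √{[p1(1-p1) + p2(1-p2)]/n}.

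For 30% against 35% at n = 436:

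- p̄ = 0.325; SE0 = √(2 × 0.325 × 0.675/436) = 0.0317
- SE1 = √[(0.2100 + 0.2275)/436] = 0.0317
- power = Φ[(0.0500 - 0.0622)/0.0317] = Φ(-0.38) = 35%

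At n = 485 the power is 38%. So about 65% (or 62%) of trials with this true rise would give no significant increase.

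Interval half-width at a 30% rate: 1.96 × √(2 × 0.30 × 0.70/436) = 6.1 points (5.8 at 485 per arm). An observed difference of zero would leave a rise of about 6 points not excluded.

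**2. What the composite does to a rise in one term.** Let B be the proportion with any other counted side effect, and assume terms are independent. The composite rate is 1 - (1 - B)(1 - p). If p goes from 10% to 20%, the composite moves by (1 - B) × 10 points. At 436 per arm:

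| Background B | Composite rates | Change (points) | Power |
|---|---|---|---|
| 30% | 37.0% to 44.0% | 7.0 | 56% |
| 50% | 55.0% to 60.0% | 5.0 | 32% |
| 70% | 73.0% to 76.0% | 3.0 | 17% |
| 80% | 82.0% to 84.0% | 2.0 | 12% |
| 95% | 95.5% to 96.0% | 0.5 | 6% |

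A direct comparison of that term, 10% against 20%, has 99% power at alpha 0.05 and 87% at 0.05/19. The composite is weaker at every background rate shown.

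**The case against.** The strongest reply is that comparison of the individual side effects is already planned. Protocol 5.1 promises it, SAP 7.4.2 says the side effects are reported separately, and SAP 6.4 counts analyses named in the protocol among the planned final analyses. A reader might infer that the plan cannot detect a rise in a single side effect, or that a bloating signal would be lost in the composite. The documents do not support that: the tabulation could show it. What is missing is a method and interval for that comparison, since SAP 7.4.1 specifies only the composite.

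A reader might also infer that the sponsor will treat p > 0.05 as proof of similarity. Nothing in the documents says so. They state the hypothesis and a test, and leave the step between them undefined. Nor is the plan a single test on 23 terms, as there are two windows with different counts.

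The figures depend on the rates chosen. For a rise from 30% to 40%, power at 436 per arm is 87%, and no document defines a 5-point rise as relevant. The background rate is unknown, and at 30% the composite keeps 56% power. These points are fair. They rule out saying that the composite cannot detect harm, but do not make it the better analysis.

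The effect-size sentence in SAP 7.2 helps only in part: it sits under the primary outcome and names no interval. Finally, the primary safety endpoint is invasive *Lactobacillus* disease and the efficacy analysis is untouched, which limits the weight of the point.

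**Conclusion.** The concern holds as a mismatch between objective and specified method. The SAP sets out to test similarity and specifies only a difference test on an any/none composite in two windows, with no interval or margin. That test cannot establish similarity, whatever the rates are. The sizes do rest on assumed rates: 35% to 38% power for 30% against 35%, and an interval of about plus or minus 6 points at 30%.

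The composite has less power than a direct comparison for a rise in one term. How much less depends on a background rate the documents do not give and on independence between terms. If the extra cases fall mainly in children who already have another side effect, the composite moves even less than shown.

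The conclusion goes no further than that. A single-term rise may still be seen in the tabulation promised by protocol 5.1. The SAP should be amended because side effects are part of a primary objective and the remedy is cheap.

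**What to change.** In SAP 7.4.1, for each window:

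- Report the risk difference, stratified by center and symptom duration, with its 95% confidence interval for the composite.
- Report the same for each listed term, which gives the comparison in protocol 5.1 a stated method. Label these intervals descriptive and unadjusted for multiplicity.
- State that similarity is judged from the upper limit of the interval and not from p > 0.05.

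A margin is optional. If one is wanted, fix and justify it before unblinding. As an illustration, at 485 per arm with no true difference and composite rates of 30% to 90%, the power to exclude a 5-point rise is 34% to 74%, and to exclude a 10-point rise 88% or more (one-sided 0.025).

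The cost is a few sentences and one more table; no new data are needed. The downside is about 20 unadjusted intervals per window, some of which may exclude zero by chance; the descriptive label is there for that reason.

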### 7.4.2 Adverse Events

Adverse events (AEs) will be recorded from the time of randomization through 35 days. Symptoms/side-effects described previously will generally not be counted as AEs, as they will be reported separately. Serious adverse events (SAEs), unexpected medically attended events, and new chronic illnesses will be reported from randomization through one year after last study dose. Adverse events will be coded using the Medical Dictionary for Regulatory Activities (MedDRA), version 14.0.

**All Adverse Events** Summaries of incidence rates (frequencies and percentages), intensity, and relationship to study of individual AEs by System Organ Class and Preferred Term (MedDRA) will be prepared. All AEs beginning after randomization but before discharge will be included. Basic summaries by assigned groups will be prepared. The DSMB may request to see more detailed tables. The occurrence of any adverse event will be considered as a dichotomous outcome and will be compared between groups using a Mantel-Haenszel test, stratified by clinical center and duration of symptoms.

**Serious Adverse Events/Deaths** SAEs/Deaths will be reported separately in a similar fashion to the more general AE reports. In addition, narratives will be available for each event.

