### 3.4 Follow Up Data Collection

Successful follow up will be maximized by obtaining multiple phone numbers for families and emergency contacts, scheduling calls and sending phone text reminders, allowing for electronic completion and centralizing all follow-up procedures at the lead institution (Washington University). Trained, experienced study staff will contact the family daily (including weekends) until both the diarrhea and vomiting have resolved and the treatment has been completed on day 5. Additional contact will be made on day 14 for outcome assessment, and months 1, 3, 6, 9 and 12 for long term safety outcomes. Study staff will use a standardized data collection form, and will inquire about ongoing symptoms, medical evaluations, treatments, child care, work absenteeism, and side effects. Detailed questioning will follow positive responses. A study diary will be provided to caregivers to use as a note-taking tool. Caregivers may also be provided an option of completing the follow-up collection electronically. Patient compliance with study drug administration will be assessed on day 5. To maximize compliance, caregivers will be reminded of the importance and method of administering the study drug. On day 14, the study site staff (not the central staff conducting the follow up) will perform a chart review for final data collection and identification of recorded adverse events during the 14 day study period. Adverse event reporting is described in detail in Section 8.3 on page 33.

Every effort will be made complete daily follow-up on the day necessary. However, if one or two days of follow-up contact is missed, data for those missed days may be collected on the next contact, if the caregiver used the home diaries or can recall the information. If all contact is missed but then the parent is contacted on day 14, follow-up data for the daily calls will be collected only if the parent diaries were used. For day 5 and 14, contact may be made within + 3 days. For month 1, 3, 6, 9, and 12 follow-up, contact may be made within  $\pm 2$  weeks.

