### 5.4.4 Loss to Follow-up

Our previous emergency department pediatric acute gastroenteritis research studies achieved telephone follow-up rates of 98% on day 3 and 96% on day 7. Similar success has been documented in other PECARN multicenter studies (91%). We estimate a 10% loss to follow-up. If daily contact does not occur, we will collect data from missed days on subsequent days when caregivers are contacted. The use of patient diaries (paper and/or electronic) and chart review will supplement parent contact. Based on our pilot trial we have devised the following strategies to maximize follow-up: all follow-up procedures will be centralized at the lead institution and conducted by experienced study staff; we will obtain multiple phone numbers from caregivers as well as emergency contacts, and we will schedule calls and send reminders prior to the call if preferred. Finally, electronic diary filing and transmission may be available for interested families.

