#### 4.1.4 Safety Population

The safety population (SAFETY) includes all subjects who receive any study drug. Reporting of results based on this population will be summarized according to treatment received. This population will be used for analysis of adverse events and (in addition to ITT) to examine safety outcomes.

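### One-year serious adverse events are planned as plain percentages with no rule for children lost before month 12, so absolute rates and risk differences will tend to be too low, by an amount the documents do not determine

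*Combined protocol and SAP*

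**What the plan says.** SAP v1.2 section 7.4.2 sets the format for adverse events: "Summaries of incidence rates (frequencies and percentages), intensity, and relationship to study of individual AEs", coded by MedDRA, with a Mantel-Haenszel comparison of any event against none. For the serious ones it adds that "SAEs/Deaths will be reported separately in a similar fashion to the more general AE reports", with a narrative for each. SAEs, unexpected medically attended events and new chronic illnesses "will be reported from randomization through one year after last study dose".

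SAP section 4.1.4 defines the population: "The safety population (SAFETY) includes all subjects who receive any study drug". It continues: "This population will be used for analysis of adverse events and (in addition to ITT) to examine safety outcomes". Completing follow-up is not a condition of membership.

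Protocol V3.0 section 3.4 describes how events are found. Around day 14, site staff "perform a chart review for final data collection and identification of recorded adverse events during the 14 day study period". Later contacts are at "months 1, 3, 6, 9 and 12 for long term safety outcomes". No chart review is planned after the one covering the first 14 days.

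On loss, protocol section 5.4.4 says "We estimate a 10% loss to follow-up", next to telephone follow-up rates for days 3 and 7. Neither document gives a 12-month figure. SAP section 5.2 says that available data are used for children who withdraw or are lost. The multiple imputation (7.2.1) and the delayed-survey sensitivity analysis (7.2.3) are written for efficacy outcomes.

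**The concern.** A percentage of dosed children treats each child as watched for the whole year. A child last reached at month 1 with nothing to report adds one to the denominator and cannot easily add to the numerator afterwards. The crude one-year percentage then falls below the true one-year risk.

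This bears on the second primary objective in SAP section 2.1.1, that the probiotic carries no association with serious adverse events. Missed events make both arms look safer and pull any absolute excess towards zero, the direction that favours the hoped-for conclusion. If one arm loses more children than the other, the comparison between arms is distorted as well.

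**Working it through.** **The plan's own figure.** The 10% loss belongs to the sample size for the two-week primary outcome (protocol section 5.3, SAP section 3.3). For 25% against 15%, two-sided 0.05 and 90% power, the pooled formula without continuity correction gives 335 per arm, or 670. Then 670/0.90 = 744, 744/0.92² = 879, and 879 × 1.02 = 897. These reproduce. There is no 12-month loss or SAE rate to reproduce, so the rest uses assumed values.

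**Formula.** Let R be the true one-year risk, f(t) the density of first events over the year and G(t) the share of children still under contact at time t. The relative understatement of the crude percentage is

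u = 1 − [∫ f(t) G(t) dt] / R.

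With events spread evenly and R small, u is close to 1 minus the mean of G. For total 12-month loss L:

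- all loss at the outset: u = L;
- steady loss over the year: u = L/2.

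Numerical integration with a constant hazard and R of 2%, 5% and 10% gives 0.049–0.050 for steady loss of 10%, 0.098–0.100 for 20% and 0.147–0.149 for 30%. The short formula is adequate.

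If a share q of events falls in the first 14 days and all of those are captured, u becomes (1 − q)L when the loss occurs at day 14, and (1 − q)L/2 when it is steady.

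| Total loss L (assumed) | Even timing: steady loss to loss at outset | Half of events by day 14: steady loss to loss at day 14 |
|---|---|---|
| 10% | 5% to 10% | 2.5% to 5% |
| 20% | 10% to 20% | 5% to 10% |
| 30% | 15% to 30% | 7.5% to 15% |

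These are relative figures. At an illustrative true risk of 5%, u = 10% gives a reported 5% × 0.90 = 4.5%, and u = 30% gives 5% × 0.70 = 3.5%.

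**Equal loss in the two arms.** The ratio is R₁(1 − u)/[R₂(1 − u)] = R₁/R₂, unchanged. The difference becomes (R₁ − R₂)(1 − u). With true risks of 4% and 2% and u = 10%, the arms show 3.6% and 1.8%: the ratio stays 2.00 and the difference falls from 2.0 to 1.8 points.

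**Unequal loss.** Suppose 10% are lost during the first 14 days of a 365-day window (14/365 = 0.038), followed by steady loss to 80% retained in one arm and 70% in the other. Mean retention is 0.038 × 0.95 + 0.962 × 0.85 = 0.854 and 0.038 × 0.95 + 0.962 × 0.80 = 0.806. Equal true rates would then show a ratio of 0.806/0.854 = 0.944, about 6% apart. At a true risk of 5% that is 4.27% against 4.03%, or 0.24 points. With 970 children, 485 per arm, the standard error of the difference is about √(2 × 0.05 × 0.95/485) = 0.014, or 1.4 points. A larger imbalance, 10% understatement in one arm and 24% in the other, would move a true ratio of 2.00 to 2.00 × 0.90/0.76 = 2.37 or 2.00 × 0.76/0.90 = 1.69.

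**The case against.** The strongest reply has four parts.

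- **Size.** The documents state neither 12-month loss nor SAE timing. SAEs include hospital admission, treatment lasts five days, and the admissions the protocol discusses surround the index illness. Events may therefore cluster early, when contact is closest. This stands, and it is why the lower rows and columns of the table matter.
- **Detection.** A reader might infer that late events are seen only when a safety contact succeeds. The documents do not support that. The chart review covers the first 14 days, sites must report SAEs to the coordinating center within 24 hours (protocol section 8.3.5), staff attempt to follow adverse events after withdrawal (section 4.4), and a later successful contact can recover an event from a missed one. These routes reduce the shortfall. None is a systematic search for a child who cannot be reached after day 14.
- **Denominator.** It is inferred from the safety population. The AE paragraph in 7.4.2 also limits its summary to events before discharge, which cannot carry over literally to a one-year window. This stands, and is itself a reason to write the rule down.
- **Inference.** With equal loss the ratio is unbiased and the test remains valid under the null. A log-rank or Poisson test would not recover events that were never seen. This stands, so there is no need to replace the Mantel-Haenszel test.

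**Conclusion.** The gap is real but limited. One-year SAEs are planned as crude percentages, apparently of all dosed children, and neither document handles incomplete 12-month contact. Absolute one-year rates and risk differences are therefore biased downward. For 10% total loss the relative understatement is about 2.5–10%, the low end requiring half the events by day 14. For 20% and 30% loss it is about 10–20% and 15–30% with even event timing, and half that if half the events come early.

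A reader might go further and say that the rates will be understated by 10–24%. That range follows arithmetically from losing 10% for good by day 14, retaining between 90% and 60% at month 12, and having events spread evenly. None of those assumptions is in the documents, and the same 10% spread over the year gives 5%. Nor do the documents show that the comparison between arms is biased: that requires unequal loss, about which they are silent. This is an inexpensive improvement to safety reporting, not a fault that undermines the planned test.

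**What to change.** In SAP section 7.4.2, for SAEs, unexpected medically attended events and new chronic illnesses:

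1. State the denominator of the percentages. In the same edit, reconcile the before-discharge limit with the one-year window, and the summaries by assigned group with section 4.1.4, which reports by treatment received.
2. Report completion of the safety contacts through month 12, by arm.
3. Add events per 100 child-years with a 95% confidence interval, counting time from randomization to the last completed safety contact, capped at 12 months after the last dose.
4. Add a one-year cumulative incidence by treatment received, censored at the last completed contact, with death counted as an event or, for non-fatal SAEs, as a competing event.
5. Keep the counts, percentages and Mantel-Haenszel test.

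The cost is SAP wording and a little extra programming, with no new visits. The added estimates assume that loss is unrelated to SAE risk, which is weaker than treating every lost child as event-free. They also need the date of the last completed contact, and the documents do not confirm that it is recorded for the month 1 to 12 contacts. That should be checked against the case report forms first.

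### SAP 7.4.2 cuts the general adverse-event summaries off at discharge and groups them by assigned arm, against the plan's own 35-day window and treatment-received rule

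*Combined protocol and SAP*

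**What the plan says.** Section 7.4.2 of SAP V1.2 contains several rules.

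- **Recording window:** "Adverse events (AEs) will be recorded from the time of randomization through 35 days".
- **Listed symptoms are set aside:** "Symptoms/side-effects described previously will generally not be counted as AEs, as they will be reported separately".
- **Longer follow-up for some events:** "Serious adverse events (SAEs), unexpected medically attended events, and new chronic illnesses will be reported from randomization through one year after last study dose".
- **General summaries**, by MedDRA class and term: "All AEs beginning after randomization but before discharge will be included. Basic summaries by assigned groups will be prepared".
- **Formal comparison**, in the same paragraph, with center and symptom duration as strata: "The occurrence of any adverse event will be considered as a dichotomous outcome and will be compared between groups using a Mantel-Haenszel test". Neither a window nor a grouping is given there.
- **Serious events and deaths:** "SAEs/Deaths will be reported separately in a similar fashion to the more general AE reports".

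Elsewhere, protocol V3.0 section 8.3.2 records adverse events until 30 days after the last dose. Protocol section 5 exempts adverse events from intention-to-treat and analyses them as treated. SAP 4.1.4 assigns adverse-event analysis to the Safety population, reported by treatment received. Protocol 5.1, under Specific Aim 2, tabulates adverse events for the final analysis and mentions no cut-off at discharge.

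**The concern.** One section gives two windows for the same events, and its grouping differs from the rule in two other places.

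The discharge limit is a poor fit for this trial. Treatment starts in the emergency department and continues at home, so a table that stops at discharge leaves out most of the exposure period and all of the follow-up after it.

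Specific Aim 2 is safety, and protocol 5.1 names the presence of any adverse event as the secondary safety outcome. For unsolicited, non-serious events, these summaries are the main place in the SAP where results appear by term and arm. A near-empty table could be read as evidence of few events when it reflects a short window. The any-event test sits in the same paragraph, so its result also depends on which sentence the programmer follows.

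**Working it through.** **1. Reproduce the window.** Protocol 4.2 gives a 5-day course and protocol 8.3.2 adds 30 days after the last dose: 5 + 30 = 35 days. This matches the opening of SAP 7.4.2, so the discharge limit is the outlier. In hours, 35 × 24 = 840.

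**2. What discharge can mean.** The SAP does not define it. The protocol uses it for leaving the emergency department (4.2 and 4.3) and for leaving hospital (8.3.6, where the end of study participation is named separately). The first dose is given in the department and 9 are taken at home, so a child sent home has had 1 of 10 planned doses.

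**3. Share of the window covered.** The documents give no length of stay; these stays are assumed.

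| Assumed stay | Share of 840 h |
|---|---|
| 2 h | 2/840 = 0.24% |
| 8 h | 8/840 = 0.95% |
| 24 h | 24/840 = 2.86% |
| 48 h | 48/840 = 5.71% |

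Taking the protocol's under-5% hospitalization figure as 5% admitted at the index visit:

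- 0.95 × 2 + 0.05 × 48 = 4.3 h, or 0.51%
- 0.95 × 8 + 0.05 × 120 = 13.6 h, or 1.62%
- 0.95 × 24 + 0.05 × 120 = 28.8 h, or 3.43%

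**4. Illustration in children.** Take 970/2 = 485 per arm. Assume a proportion *p* has an unsolicited event by day 35 and that the event rate is constant. Then H = −ln(1 − p), and the expected number in the table is 485 × [1 − exp(−H × share)].

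| Assumed p | By day 35 | Share 0.51% | Share 3.43% |
|---|---|---|---|
| 10% | 48.5 | 0.26 | 1.75 |
| 30% | 145.5 | 0.88 | 5.89 |

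**5. Grouping.** SAP 4.1.4 adds the intention-to-treat population only for safety outcomes. SAP 2.2.2 lists those as side effects and invasive *Lactobacillus rhamnosus* disease ("The occurrence of invasive disease (including meningitis and bacteremia) from" that organism), not general adverse events. The intention-to-treat population in SAP 4.1.2 also includes children who received no study drug. The two groupings therefore differ whenever a child received the other product or none. No count of such children is given.

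**6. What is not affected.** Side effects have their own windows and test in SAP 7.4.1: "the initial disease window (through day 14, or until resolution of symptoms) and through day 35 (which includes the initial window"). Serious events, unexpected events needing medical attention and newly arising chronic illness run to one year. Invasive disease is a separate outcome.

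**7. Current text.** The same sentences stand in SAP V1.1, and the summary of changes to V1.2 does not touch them.

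**The case against.** The sentence does not contain the word only, its paragraph is headed as covering all adverse events, and the section opens with 35 days. If discharge meant leaving the study, the window conflict would vanish. Protocol 5.1 tabulates adverse events without a discharge limit, and SAP 6.4 commits to the analyses in both documents, so a full table is arguably planned anyway. The assigned-arm summaries may be meant for the DSMB, since the next sentence mentions that board, and nothing forbids as-treated tables as well. The population left is small once the 23 listed side effects and the events followed to one year are removed.

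Part of this stands. The restriction is the natural reading, not an explicit exclusion, and discharge is undefined. The scope is narrow. The per-arm counts in step 4 illustrate assumptions; they are not estimates from the documents. The 5% input is also uncertain: protocol 4.2 applies the under-5% figure to enrolled children generally, while protocol 4.3 applies it to children hospitalized after going home, who would not lengthen the stay before discharge.

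None of it removes the conflict. Neither protocol use of the word comes near 35 days for most children: even a 48-hour stay covers 5.7%. Protocol 5.1 and SAP 6.4 add a competing instruction without correcting this one. Dual programming (SAP 5.7) would not catch a rule that both programmers follow literally. SAP 1.2 requires unplanned analyses to be labelled as such, so a 35-day table could be challenged as a departure from the written rule.

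**Conclusion.** The concern holds and should be corrected before the safety tables are programmed. The text is wrong as written, not merely short of detail: followed literally, it truncates a safety outcome that the protocol names.

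On its doses the table would reach about 1 of 10. On time it would reach roughly 0.5% to 3.4% of the window, given the assumed stays and the 5% admission reading. Share of time equals share of events only if the event rate is constant. That the cut is severe does not depend on the exact stay; the particular percentages do.

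The grouping conflict is equally plain in the text, but its effect cannot be sized. The consequences are confined mainly to unsolicited, non-serious events and to the any-event comparison. Efficacy, the primary safety endpoint and the collection of adverse events are untouched.

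**What to change.** In SAP 7.4.2, replace the two conflicting sentences with one rule, for example: *Adverse events with onset from randomization through day 35 are summarized in the Safety population by treatment received.*

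State the same window and grouping for the any-event Mantel-Haenszel test. Repeat the existing one-year window in the paragraph on serious events and deaths. That window already governs, but restating it prevents the loose cross-reference to the general reports from being read as importing the discharge limit. If an assigned-arm table is wanted for the DSMB, label it supplementary.

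The cost is SAP wording only. Adverse events are already collected to day 35, and the longer-followed events to one year. The change restores rules that the documents already contain and involves no choice about clinical management.
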